5.4.3. Electrocardiograms

A 12-lead Electrocardiogram (ECG) with categorical results (normal; abnormal, not clinically significant; abnormal, clinically significant) will be summarized in the shift summary from baseline to worst post baseline. Post baseline includes non-missing records collected (scheduled and unscheduled) after the first dose of study treatment until 30 days following the last dose of study treatment. QT measurements corrected by heart rate will be used for the data analysis and interpretation. QTc interval will be calculated using Fridericia’s correction. The formula is:

$$\text{Fridericia's correction: } QT_cF = QT / RR^{0.33}$$

where unit of QT is milliseconds (msec) and unit of RR is second (sec). The number and percentage of patients in QT and QTcF (QT and QTcF interval: ≤ 450 msec, > 450 - ≤ 480 msec, > 480 - ≤ 500 msec, and > 500 msec) will be summarized at baseline and maximum post baseline. Categories of maximum changes from baseline (≤ 30 msec, > 30 - ≤ 60 msec, > 60 msec) will be summarized as well.

An ECG result listing that including PR interval, RR interval, QT, QTc, QRS duration and Heart Rate will also be provided.

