**Table 7: Schedule of Assessments (Arm 1, Combination of DSP-7888 Dosing Emulsion and Nivolumab [14-Day Study Cycles])**

Tests and Procedures	Pre-Screening	Pre-Study Evaluation	On-Study Evaluations a									End of Treatment	Follow-Up For OS
			Cycle 1		Cycle 2		Cycle 3	Cycle 4	Cycle 5	Cycle 6	Cycle 7+		
Week			0	1	2	3	4	6	8	10	12+	30 days after last DSP-7888 Dosing Emulsion dose	Every 3 months after date off treatment
Day	Any time before enrollment	Within 28 days prior to first dose of study drug	1	8	15	22	29	43	57	71	85+		
Window		28 days	±2 days	±2 days	±2 days	±2 days	±2 days	±2 days	±2 days	±2 days	±2 days		
Pre-screening consent	X												
HLA-typing (A/B locus and DRB1 locus)	X												
Informed consent		X											
Inclusion/exclusion review		X											
Medical and cancer history		X											
Physical examination		X	X		X c		X c	X					
Serum pregnancy test, if applicable		X											
ECOG performance status		X			X		X	X	X	X	X	X	
Complete vital signs		X	X		X		X	X	X	X	X	X	
Body weight		X	X		X		X	X	X	X	X	X	
Hematology		X		X	X	X	X	X	X	X	X	X	
Clinical chemistry		X		X	X	X	X	X	X	X	X	X	
Thyroid function test		X			X		X	X	X	X	X	X	
Urinalysis		X		X	X	X	X	X	X	X	X	X	
Pulse oximetry		X	X		X		X	X	X	X	X	X	
Blood samples for Hepatitis B/C & HIV		X											
ECHO/MUGA		X			X			X			X d	X	
12-lead electrocardiogram		X	X e		X e			X			X f	X	
Tumor tissue samples for biomarkers g		X h									X i		
Tumor tissue samples for future biomarker analysis j		X									X i		

Tests and Procedures	Pre-Screening	Pre-Study Evaluation	On-Study Evaluations a									End of Treatment	Follow-Up For OS
			Cycle 1		Cycle 2		Cycle 3	Cycle 4	Cycle 5	Cycle 6	Cycle 7+		
Week			0	1	2	3	4	6	8	10	12+	30 days after last DSP-7888 Dosing Emulsion dose	Every 3 months after date off treatment
Day	Any time before enrollment	Within 28 days prior to first dose of study drug	1	8	15	22	29	43	57	71	85+		
Window		28 days	±2 days	±2 days	±2 days	±2 days	±2 days	±2 days	±2 days	±2 days	±2 days	+7 days b	
Blood samples for CTL induction k		X l			X m		X m		X m		X m,n	X	
Blood samples for future biomarker analysis o		X l			X m		X m		X m		X m,n	X	
Concomitant medications		X	X	X	X	X	X	X	X	X	X	X	

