**Table 9: Schedule of Assessments (Phase 2, Combination of DSP-7888 Dosing Emulsion and Pembrolizumab for Ovarian Cancer)**

Period	Pre-screening	Screening period	Treatment Period (All procedure must be performed PRIOR to injection of study treatment)										Follow-up Period		Notes
			1			2			3	4	5+*	EOT (30 day after last dose)	Disease follow up**	Survival Follow up	
			1	8	15	1	8	15	1	1	1				
			0	1	2	3	4	5	6	9	12				
Scheduling Window (Days)	-	-28 to 1*	0	±2	±2	±2	±2	±2	±3	±3	±7	+7 a	±7	±14	*Procedures in screening should be completed within 28 days from Cycle 1 Day1
Study Drug Administration															
DSP-7888 Dosing Emulsion			X	X	X	X			X	X	X				
Pembrolizumab						X			X	X	X				
Administrative procedure															
HLA screening informed consent	X														
Informed Consent*		X													*Main informed consent and informed consent for future biomarker (optional) for willing participants
Inclusion and Exclusion criteria		X													
Demography and Medical History		X*													*including COVID-19 history and vaccination history
Prior and Concomitant Medications		X	X	X	X	X			X	X	X	X			
Cancer history and Cancer Prior Treatment		X													

Period	Pre-screening	Screening period	Treatment Period (All procedure must be performed PRIOR to injection of study treatment)										Follow-up Period		Notes	
			1			2			3	4	5+*	EOT (30 day after last dose)	Disease follow up**	Survival Follow up		
Treatment Cycle	Day	Week (from 1 st dose)	1	8	15	1	8	15	1	1	1					
Scheduling Window (Days)	-	-28 to 1*	0	±2	±2	±2	±2	±2	±2	±3	±3	±7	+7 a	±7	±14	
New anticancer therapy														X	X	*Every 12 weeks up to 105 weeks and/or on an ad-hoc basis for safety or regulatory purposes, or a prespecified analysis.
Safety assessment																
Physical Examination*		X	X			X				X	X	X	X			*Inspection of prior injection site will be done
Vital Sign and Weight		X*	X	X	X	X				X	X	X	X			*Height will be measured only at screening
12-lead ECG		X								X			X			
ECHO/MUGA		X														
ECOG performance status		X	X	X	X	X				X	X	X	X			
Adverse Events	X*	X**	X	X	X	X				X	X	X	X**			* SAE related to study procedure will be reported to ██████████ Safety **AE must be collected from the date of main ICF to 30 days after last dose

Period	Pre-screening	Screening period	Treatment Period (All procedure must be performed PRIOR to injection of study treatment)										Follow-up Period		Notes	

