Blood samples for future biomarker (optional)*		X				X			X		X**	X					*Only patients who provides informed consent for future biomarker samples to be taken prior to dosing. Serum, PBMC and ctDNA (plasma) are included as a blood sample. PBMC will be prepared from whole blood at Central Laboratory. The whole blood sample for PBMC preparation should be shipped from clinical site to central laboratory on the sample collection date. **Cycle 5, 7, 9 and subsequent assessments every 4 cycles (Cycle 13, 17, 21 etc.) ctDNA only at screening, Cycle 3 Day1, Cycle 5 Day1, next visit when patients have PR or CR with RECIST criteria, and EOT.

Period	Pre-screening	Screening period	Treatment Period (All procedure must be performed PRIOR to injection of study treatment)										Follow-up Period		Notes
			1			2			3	4	5+*	EOT (30 day after last dose)	Disease follow up**	Survival Follow up	
			1	8	15	1	8	15	1	1	1				
			0	1	2	3	4	5	6	9	12				
Scheduling Window (Days)	-	-28 to 1*	0	±2	±2	±2	±2	±2	±3	±3	±7	+7 a	±7	±14	*Procedures in screening should be completed within 28 days from Cycle 1 Day1
Tumor tissue collection		X*										X**	X**		* Fresh biopsy (if medically feasible), archival tumor block, or newly cut slides are required at screening. **Cycle 5, or EOT if earlier, if medically feasible
Tumor samples for future biomarker (optional)		X*										X**	X**		*Only patients who provides informed consent for future biomarker. Either archival tissue or fresh biopsy samples will be collected and a total of 6 to 8 slides will be sent to the central laboratory for analyses **Cycle 5, or EOT if earlier, if medically feasible

a Complete End of Treatment assessment procedures before patient receives new anti-cancer treatment.

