### **8.3. Dose Modification**

Any study treatment may be interrupted at any time for any grade toxicity considered intolerable by the patient, based on the investigator's and patient's judgment.

In the case of any patient who has missed 4 or more consecutive doses of either study drug, that study drug should be permanently discontinued, but the patient may continue on the other nonmissed study drug. If the patient is experiencing clinical benefit and, in the opinion of the investigator it is in the patient's best interest to remain on study, the patient may continue treatment on a case-by-case basis, after documented discussion with the Sponsor.

Dose modification by treatment is described in the following sections.

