3.2. Safety Set

The Safety Set (SS) consists of all patients who receive at least 1 full or partial dose of study treatment (DSP-7888 Dosing Emulsion, nivolumab, or pembrolizumab). Patients will be classified according to the treatment received (dose level and schedule), where treatment received is defined as the actual treatment if the patients took at least 1 dose of that treatment or the first treatment received if the assigned treatment was never received.

Safety analysis set will be used for all safety related analyses such as AE, concomitant medication, laboratory tests, and vital signs and drug exposure evaluation.

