5.4.2. Clinical Laboratory Evaluations

All samples will be analyzed at a central laboratory and collected per Schedule of Assessments in the protocol. Local laboratories may be used as deemed necessary by the Investigator in order to make treatment related decisions.

The results of laboratory parameters will be graded according to NCI CTCAE v4.03 for below parameters (Table 12). For patients with both baseline and post baseline assessments, a summary of shift from baseline CTCAE grade to maximum postbaseline CTCAE grade will be provided. All records on or after the first dose (scheduled and unscheduled) until 30 days following the last dose of study drug will be considered as post baseline. Additional parameters may be added for the shift tables. Both scheduled and unscheduled laboratory test results will be included in the shift tables.

For the purposes of summarization in both the tables and listings, all laboratory values will be converted to standardized units. If a lab value is reported using a non-numeric qualifier (e.g., less than (<) a certain value, or greater than (>) a certain value), the given numeric value will be used in the summary statistics, ignoring the non-numeric qualifier.

Table 9: CTCAE Lab Grading Parameters.

	↓	↑
HEMATOLOGY	Anemia	
HEMATOLOGY	White blood cell decreased	
HEMATOLOGY	Lymphocyte count decreased	
HEMATOLOGY	Neutrophil count decreased	
HEMATOLOGY	Platelet count decreased	
CHEMISTRY		Alanine aminotransferase increased

CHEMISTRY	Hypoalbuminemia	
CHEMISTRY		Alkaline phosphatase increased
CHEMISTRY		Aspartate aminotransferase increased
CHEMISTRY		Blood bilirubin increased
CHEMISTRY		Blood Urea Nitrogen Increased
CHEMISTRY	Hypocalcemia	Hypercalcemia
CHEMISTRY		Creatinine increased
CHEMISTRY	Hypoglycemia	Hyperglycemia
CHEMISTRY	Hypomagnesemia	Hypermagnesemia
CHEMISTRY	Hypophosphatemia	
CHEMISTRY	Hypokalemia	Hyperkalemia
CHEMISTRY	Hyponatremia	Hypernatremia

Blood Urea Nitrogen Increased is not in CTCAE grading, SDPO will define as grade 1 is 23 – 26 mg/dL, grade 2 is 27-31 mg/dL, grade 3, >31 mg/dL.

Listings of hematology and biochemistry, urinalysis and coagulation will be provided, including the test result, units, normal range, change from baseline, and CTCAE grade if available.

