5.4.4. Vital Signs

Body temperature will be summarized in °C. If body temperature is recorded as °F, then temperature will be converted to °C using:

Temperature (°C) = 5/9 (Temperature [°F]-32).

Summaries of post baseline markedly abnormal vital signs, including systolic blood pressure, diastolic blood pressure, pulse rate, weight change, and temperature will be presented. Markedly abnormal ranges for vital signs parameters are given in Table 13 . Post baseline includes non-missing records from both scheduled and unscheduled visits after the first dose of study drug until 30 days following the last dose of study treatment.

Table 10: Markedly Abnormal Ranges for Vital Signs

Parameter	Markedly Abnormal (Low)	Markedly Abnormal (High)
Systolic Blood Pressure	
 • Absolute value ≤ 90 mmHg for post baseline, or • a decrease from baseline ≥ 20 mmHg for change from baseline 	
 • Absolute value ≥ 180 mmHg for post baseline, or • an increase from baseline ≥ 20 mmHg for change from baseline
Diastolic Blood Pressure	
 • Absolute value ≤ 50 mmHg for post baseline, or • a decrease from baseline ≥ 15 mmHg for change from baseline 	
 • Absolute value ≥ 105 mmHg for post baseline, or • an increase from baseline ≥ 15 mmHg for change from baseline
Pulse	
 • Absolute value ≤ 50 bpm for post baseline, or • a decrease from baseline ≥ 15 bpm for change from baseline 	
 • Absolute value ≥ 120 bpm for post baseline, or • an increase from baseline ≥ 15 bpm for change from baseline
Weight Change	Weight loss from baseline $\geq 20\%$	Weight gain from baseline $\geq 20\%$
Temperature	$\leq 35^{\circ}\text{C}$ post baseline only	$\geq 40^{\circ}\text{C}$ post baseline only

A listing of vital signs results will also be presented using the Safety Set.

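### The SAP's post-baseline cut-off for labs, ECGs and vital signs is day 30 after the last dose, but the protocol allows the End of Treatment visit on days 30 to 37, so compliant visits on days 31 to 37 can fall outside the summary tables

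*SAP*

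**What the plan says.** **Visit timing.** Protocol Table 9 (Phase 2) heads the EOT column "EOT (30 day after last dose" and gives it a window of +7 days. Tables 7 and 8 (Phase 1b Arms 1 and 2) use the same +7-day window but time the visit as "30 days after last DSP-7888 Dosing Emulsion dose". None of the three tables has a minus side. A footnote can bring the visit forward: "Complete End of Treatment assessment procedures before patient receives new anti-cancer treatment". All three tables schedule hematology, chemistry, vital signs and a 12-lead ECG at EOT.

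**Analysis cut-off.** For laboratory tests, SAP 5.4.2 says that records "until 30 days following the last dose of study drug will be considered as post baseline". For ECGs, SAP 5.4.3 takes records "after the first dose of study treatment until 30 days following the last dose of study treatment". For vital signs, SAP 5.4.4 takes those "after the first dose of study drug until 30 days following the last dose of study treatment".

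**Which last dose.** SAP 3.2 names the components as "study treatment (DSP-7888 Dosing Emulsion, nivolumab, or pembrolizumab". Protocol 8.3 says that after four or more consecutive missed doses of one drug, "the patient may continue on the other nonmissed study drug". The last checkpoint-inhibitor dose can therefore come later than the last DSP-7888 dose.

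**Other relevant rules.** SAP 4.3.4 includes scheduled and unscheduled visits in maximum post-baseline summaries unless another section specifies otherwise. It keeps every record in the listings, whether or not it lies in the reporting period. The SAP has no visit-window rule for EOT.

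**The concern.** The protocol asks for a safety visit at day 30 or up to a week later, and the analysis plan stops counting at day 30. The two windows are each reasonable alone, but they share a single day. A site that sees the patient on day 33 has followed the protocol, yet under the SAP as written those results do not enter the post-baseline summaries.

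This matters more than usual because SAP version 3.0 drops the efficacy and biomarker analyses and makes the final report a synoptic, safety-focused one. The tables affected are the laboratory shift to maximum CTCAE grade, the ECG shift to worst post-baseline result, the QTcF maximum and maximum-change categories, and the markedly abnormal vital signs.

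The adverse-event tables are not a dependable substitute. SAP 5.4.1 also ends treatment-emergent onset at 30 days, unless the event is serious and related. A non-serious abnormality first detected on day 33 could therefore appear only in a listing.

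**Working it through.** No sample size, power or error rate depends on this point, and the plan states no figure to reproduce. The check is a count of days.

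**1. Permitted EOT days.** From Tables 7, 8 and 9: day 30 to day 30 + 7 = 37. Count = 37 − 30 + 1 = 8 days.

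**2. Overlap with the SAP cut-off, same last dose on both clocks.** The SAP keeps day 30 or earlier. Overlap = 1 day (day 30). Excluded = 8 − 1 = 7 days (31 to 37), and 7/8 = 87.5% of the permitted days. This case covers Phase 2, where Table 9 refers simply to the last dose. It also covers Phase 1b when both drugs stop together; in maintenance, Tables 7 and 8 schedule them on the same days.

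**3. From days to visits.** Let s be the share of on-time EOT visits done on day 30. The share left out is 1 − s. The documents do not give s, so I show the range:

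| s | Share of on-time visits left out (1 − s) |
|---|---|
| 1 | 0% |
| 0.75 | 25% |
| 0.5 | 50% |
| 0.125 (visits spread evenly over the 8 days) | 87.5% |
| 0 | 100% |

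Visits brought forward to day 30 or earlier because new anticancer therapy is starting are kept and lie outside this calculation.

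**4. Phase 1b, when the checkpoint inhibitor outlasts DSP-7888.** Let L be the days from the last DSP-7888 dose to the last checkpoint-inhibitor dose. An EOT visit on day d after DSP-7888 is day d − L after the last study drug, so it is left out only if d − L > 30. Counting over d = 30 to 37:

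| L (days) | Permitted days left out |
|---|---|
| 0 | 7 of 8 |
| 3 | 4 of 8 |
| 6 | 1 of 8 |
| 7 or more | 0 of 8 |

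One further nivolumab dose (14 days later) or pembrolizumab dose (21 days later) brings every on-time EOT visit inside the cut-off.

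**5. Where a lost visit matters.** In Table 9 the ECG row is marked at screening, at one on-treatment visit and at EOT. The on-treatment mark lines up with Cycle 3 (Week 6) in the physical-examination row.
- Patient who stops before Cycle 3: one scheduled post-baseline ECG, at EOT. If it is done on days 31 to 37, 1 − 1 = 0 remain in the tables.
- Patient who has the Cycle 3 ECG: two scheduled post-baseline ECGs. If EOT is done on days 31 to 37, 2 − 1 = 1 remains.

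Hematology and chemistry, by contrast, are drawn on Day 1 of each Phase 2 cycle, and vital signs are taken at every dosing visit. For these, EOT is one of several values feeding a maximum.

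**6. Does another rule bring the results back?** SAP 4.3.4 defers to sections that specify otherwise, and 5.4.2 to 5.4.4 do specify a limit. It keeps the records in listings but does not return them to the tables.

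**The case against.** The strongest reply is that 30 days is a deliberate common safety window. SAP 5.4 states it for safety as a whole, the treatment-emergent definition uses it, and the protocol collects adverse events to the same point. The tables are descriptive, with no hypothesis test, and most laboratory and vital-sign maxima rest on many earlier values. This is a good reason to leave the adverse-event window as it is, and it limits the weight of the point. It does not settle the mismatch: an event can have its onset on any day, whereas the protocol times these measurements at day 30 or later, so the common window cuts through the visit meant to supply them.

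Three stronger readings are tempting, and the documents do not support them.
- A reader might infer from 7 of 8 days that most EOT safety data are lost. That fraction counts calendar days, not patients. Day 30 is the nominal target, the visit-day distribution is not given, and some visits will be brought forward.
- A reader might infer that the data are discarded, or that a patient vanishes from the QTcF tables. SAP 4.3.4 keeps all records in listings, SAP 5.4.3 also summarizes QTcF at baseline, and unscheduled post-baseline ECGs count.
- A reader might infer that nothing is lost only if every EOT visit falls by day 30. Step 4 of the working shows this is false in Phase 1b.

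**Conclusion.** The mismatch is real and should be corrected, but its effect is limited to summary tables and its size in patients is unknown. With a shared last dose, 7 of the 8 permitted EOT days fall outside the SAP cut-off. The share of on-time visits affected lies between 0 and 100%. Visits brought forward to day 30 or earlier lose nothing, nor do Phase 1b patients whose checkpoint inhibitor continued at least 7 days beyond DSP-7888.

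The practical weight is in the Phase 2 ECG tables, where a patient who stops before Cycle 3 may contribute no scheduled post-baseline ECG. For laboratory tests and vital signs the likely effect is smaller.

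This rests on two readings: that the on-treatment ECG mark in Table 9 belongs to Cycle 3, and that study drug in SAP 5.4.2 and 5.4.4 means any of the three agents, as SAP 3.2 defines study treatment.

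**What to change.** In SAP 5.4.2, 5.4.3 and 5.4.4, define post-baseline records as those up to 30 days after the last dose of any study drug, plus the scheduled EOT visit if it is done within its protocol window (up to day 37). Add a matching sentence to SAP 5.4 so that the general safety statement and its subsections agree. Tying the extension to the visit window gives it an upper limit, so a late, out-of-window visit does not enter the tables through it. Add no exclusion for new anticancer therapy: these sections have none now, and one could remove records that currently count. Leave the 30-day treatment-emergent window unchanged.

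After the change, 0 of the 8 permitted EOT days fall outside, against 7 of 8 now when the last dose is shared. The cost is SAP wording and one programming rule, with no new data, visits or patients. The downside is that laboratory tests, ECGs and vital signs would use a slightly longer window than treatment-emergent adverse events, which a table footnote can state. The change is best made before the final tables are run, so that the cut-off is not chosen with results in view.

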5.4.4. Vital Signs

Body temperature will be summarized in °C. If body temperature is recorded as °F, then temperature will be converted to °C using:

Temperature (°C) = 5/9 (Temperature [°F]-32).

Summaries of post baseline markedly abnormal vital signs, including systolic blood pressure, diastolic blood pressure, pulse rate, weight change, and temperature will be presented. Markedly abnormal ranges for vital signs parameters are given in Table 13 . Post baseline includes non-missing records from both scheduled and unscheduled visits after the first dose of study drug until 30 days following the last dose of study treatment.

Table 10: Markedly Abnormal Ranges for Vital Signs

Parameter	Markedly Abnormal (Low)	Markedly Abnormal (High)
Systolic Blood Pressure	
 • Absolute value ≤ 90 mmHg for post baseline, or • a decrease from baseline ≥ 20 mmHg for change from baseline 	
 • Absolute value ≥ 180 mmHg for post baseline, or • an increase from baseline ≥ 20 mmHg for change from baseline
Diastolic Blood Pressure	
 • Absolute value ≤ 50 mmHg for post baseline, or • a decrease from baseline ≥ 15 mmHg for change from baseline 	
 • Absolute value ≥ 105 mmHg for post baseline, or • an increase from baseline ≥ 15 mmHg for change from baseline
Pulse	
 • Absolute value ≤ 50 bpm for post baseline, or • a decrease from baseline ≥ 15 bpm for change from baseline 	
 • Absolute value ≥ 120 bpm for post baseline, or • an increase from baseline ≥ 15 bpm for change from baseline
Weight Change	Weight loss from baseline $\geq 20\%$	Weight gain from baseline $\geq 20\%$
Temperature	$\leq 35^{\circ}\text{C}$ post baseline only	$\geq 40^{\circ}\text{C}$ post baseline only

A listing of vital signs results will also be presented using the Safety Set.

5.5. Efficacy Analyses

As the study was terminated for phase 2 portion due to the interim monitoring for efficacy. The final CSR will focus on the safety updates for the study as a synoptic CSR. As a result, there will no analysis included for efficacy portion. The timepoint overall response evaluation, BOR, ORR, DCR and DOR based on RECIST 1.1 will be listed.

